4.3 NEUTROPENIA

If patients develop grade 4 neutropenia, begin treatment with G-CSF. Administer 300 mcg for all patients. Once G-CSF is instituted, continue to administer it prophylactically for subsequent (days 2-6 each week) doses on all cycles. Give G-CSF for days 2-6 each week, stopping it the day before the next dose. On dose 4, give G-CSF for days 2-6 after the dose.

5 DATA COLLECTION AND EVALUATION

5.1 DATA COLLECTION

Data will be collected and entered into the NCI C3D clinical trials database. Complete records must be maintained on each patient including supplementary information obtained from outside laboratories, radiology reports, or physician's records. These records will serve as the primary source material that forms the basis for the research record. The primary source documentation will assure the following:

- The patient satisfied each eligibility criterion.
- Signed informed consent was obtained prior to registration and treatment.
- Treatment was given according to protocol or any protocol violations documented and justified.
- Toxicity and response were assessed according to protocol.
- Drug accountability records were kept on each patient.

5.2 DATA REPORTING

This study will be monitored by the Clinical Data Update System (CDUS) version 3.0. Cumulative CDUS data will be submitted quarterly to CTEP by electronic means. Reports are due January 31, April 30, July 31 and October 31. Instructions for submitting data using the CDUS can be found on the CTEP web site (<http://ctep.cancer.gov/reporting/cdus.html>).

Effective Amendment J (version date 01/16/2015), the protocol has been completed with CTEP.

5.3 RESPONSE CRITERIA

Response criteria for lymphomas as per Cheson criteria. [18] with modifications as described below. Responses must last for at least 4 weeks off treatment.

- Complete response (CR): Complete disappearance of all detectable clinical and radiographic evidence of disease and disappearance of all disease-related symptoms if present before therapy, and normalization of those biochemical abnormalities (e.g. LDH) definitely assignable to the lymphoma. All lymph nodes must have regressed to normal size (≤ 1.5 cm in greatest diameter if > 1.5 cm before therapy). Previously involved nodes that were 1.1 to 1.5 cm in greatest diameter must have decreased to ≤ 1 cm or by more than 75% in the sum of the products of the greatest diameters (SPD). Spleen, if considered to be enlarged before therapy, must have regressed in size and not be palpable on physical examination. The bone marrow must show no evidence of disease by

histology. Flow cytometric, molecular or cytogenetic studies will not be used to determine response.

- Complete response unconfirmed (CRu): As per CR criteria except that if a residual node is > 1.5 cm, it must have regressed by $> 75\%$ in SPD. Lymphocyte aggregates within the bone marrow must be negative for B-cell markers (e.g. L26).
- Partial response: $\geq 50\%$ decreased in SPD of 6 largest dominant nodes or nodal masses. No increase in size of nodes, liver or spleen and no new sites of disease. Splenic and hepatic nodules must regress by $\geq 50\%$ in the SPD. Bone marrow is irrelevant for determination of a PR.
- Definition of progressive disease (PD): Defined by at least one of the following: $\geq 25\%$ increase in the sum of the products of at least two lymph nodes, appearance of new lymph nodes, $\geq 50\%$ increase in the size of the liver and/or spleen as determined by measurement below the respective costal margin, appearance of new palpable hepatomegaly or splenomegaly that was not previously present, $\geq 50\%$ increase in the absolute number of circulating lymphocytes.
- Definition of stable disease: (SD) will be characterized by not meeting any of the criteria outlined above.

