- One of the great challenges in developing flavopiridol and applying it clinically has been determining its optimal dosing schedule. Following several different dosing schedules, one strategy that has been very promising in CLL is the application of so-called hybrid schedules of the drug (an infusion for an intermediate time following a bolus dose).

Objectives:

- Assess the toxicity and safety of administration of this hybrid schedule
- Assess the response rate of the hybrid schedule of flavopiridol in relapsed MCL and DLBCL

Eligibility:

- Relapsed MCL or DLBCL
- ECOG P.S. ≤ 2
- Age ≥ 18 years
- HIV serology negative

Design:

- Phase I/II
- Phase I portion consists of 3-4 dose levels of 3-6 patients each
- Administer weekly X 4 and then 2 weeks off (1 cycle). Restage after every 2 cycles. Continue if CR, PR or SD for up to 6 cycles. Dose reductions for toxicity will be addressed in the protocol.
- Phase II portion of the study will be a Simon optimal two-stage design: designed to rule out 20% response rate ($p_0=0.20$) in favor of a 45% response rate ($p_1=0.45$)
- The maximum sample size to be accrued for this study will be 71 patients.

TABLE OF CONTENTS

PRÉCIS	3
TABLE OF CONTENTS	4
1 INTRODUCTION	6
1.1 Study Objectives	6
1.2 Background and Rationale	6
2 ELIGIBILITY ASSESSMENT AND ENROLLMENT	11
2.1 Eligibility Criteria	11
2.2 Research Eligibility Evaluation	11
2.3 Patient Registration	12
3 STUDY IMPLEMENTATION	12
3.1 Study Design:	12
3.2 Drug Administration	13
3.3 Treatment Modifications:	15
3.4 Study Calendar	19
3.5 Off Study Criteria	21
3.6 Post Treatment Evaluation	21
4 SUPPORTIVE CARE	21
4.1 Tumor Lysis Syndrome	21
4.2 Anti-emesis	22
4.3 Neutropenia	22
5 DATA COLLECTION AND EVALUATION	22
5.1 Data collection	22
5.2 Data reporting	22
5.3 Response criteria	22
5.4 Toxicity Criteria	23
6 STATISTICAL CONSIDERATIONS	23
6.1 Data, Safety and Monitoring Board	24
7 HUMAN SUBJECTS PROTECTIONS	24
7.1 Rationale for subject selection	24
7.2 Evaluation of benefits and risks/discomforts	25
7.3 Risk/Benefit Analysis	25

7.4	Consent and assent	25
8	SAFETY REPORTING REQUIREMENTS/DATA AND SAFETY MONITORING PLAN	
	25	
8.1	Definitions.....	25
8.2	NCI-IRB and Clinical Director Reporting	25
8.3	CTEP Adverse Event Reporting Requirements	26
8.4	The Comprehensive Adverse Event and Potential Risks list (CAEPR).....	26
8.5	Adverse Event Characteristics	29
8.6	Expedited Adverse Event Reporting.....	29
8.7	Routine Adverse Event Reporting.....	31
8.8	Secondary AML/MDS	31

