3.2 DRUG ADMINISTRATION

3.2.1 Phase 1 Dosing and Schedule

The Phase I dose escalation will follow one of two different escalation rates shown in Tables 1 and 2 below. If DLT is observed in 0/3 or 1/6 patients on dose level 1, subsequent patients will be enrolled according to the paradigm described in Table 1 below. If DLT is observed in 2/6 patients on dose level 1, subsequent patients will be enrolled according to the paradigm described in Table 2 below.

Flavopiridol dose levels

Table 1	Cycle 1, Week 1		Cycle 1, Weeks 2–4, AND All weeks During All Subsequent Cycles	
Dose level	Bolus x30 minutes IV	Continuous infusion x 4 hrs	Bolus x30 minutes IV	Continuous infusion x 4 hrs
1	30mg/m ²	30mg/m ²	30mg/m ²	50mg/m ²
2	30mg/m ²	50mg/m ²	30mg/m ²	50mg/m ²
3	30mg/m ²	50mg/m ²	40mg/m ²	60mg/m ²
4	40mg/m ²	60mg/m ²	40mg/m ²	60mg/m ²

Table 2	Cycle 1, Week 1	Cycle 1, Weeks 2–4, AND All weeks During All Subsequent Cycles

Dose level	Bolus x30 minutes IV	Continuous infusion x 4 hrs	Bolus x30 minutes IV	Continuous infusion x 4 hrs
1	30mg/m ²	30mg/m ²	30mg/m ²	50mg/m ²
1A	25mg/m ²	25mg/m ²	30mg/m ²	50mg/m ²
1B	25mg/m ²	25mg/m ²	40mg/m ²	60mg/m ²

- Administer weekly x 4 consecutive weeks, followed by 2 weeks without flavopiridol treatment for a cycle duration of 6 weeks (1 cycle).
- For cycles 2-6, administer the doses given during cycle 1, weeks 2-4 for all doses.
- Administer up to 6 cycles if no disease progression.
- Restage all positive sites of disease after every 2 cycles, except bone marrow which should be repeated after other sites have achieved a CR.
- Administer flavopiridol in the inpatient unit on cycle 1, dose 1 (bolus and infusion).
- Unless medically contraindicated, all patients will receive allopurinol 300 mg per day on cycle 1 x 5 days. All patients should receive at least 200 mL/hr 0.9% Sodium Chloride Injection for 6 hours prior to the first flavopiridol dose. Detailed required guidelines for Tumor Lysis Syndrome prevention is shown in section 4.3.
- If cycle 1, dose 1 is tolerated without TLS, subsequent doses may be administered outpatient.

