3.2.2 Phase 2 Dosing

- Dose will be the MTD from the phase I portion.
- Administer weekly x 4 consecutive weeks, followed by 2 weeks without flavopiridol treatment for a cycle duration of 6 weeks (1 cycle).
- For all weeks of all cycles after cycle 1, patients will receive the dose administered on cycle 1, weeks 2-4.
- Administer up to 6 cycles if no disease progression.
- Restage all positive sites of disease after every 2 cycles, except bone marrow which should be repeated after other sites have achieved a CR.

3.2.3 Definition of Dose Limiting Toxicity:

Dose-limiting toxicity will be determined during the first cycle of treatment and is defined as:

- any grade 3 or greater non-hematologic toxicity excluding transient liver function abnormalities that resolve spontaneously within 10 days and/or transient electrolyte abnormalities that are not life-threatening, or fatigue
- grade 4 thrombocytopenia (< 25,000/mcL) persisting for 4 or more days

- grade 4 neutropenia ANC < 500/mcL persisting for 7 or more days despite the institution of G-CSF
- inability to continue with cycle 2 by 3 weeks after the end of cycle 1. Exceptions to this (i.e. accidents, family emergencies, etc) will be evaluated on a case-by-case basis.
- irreversible \geq grade 2 non-hematologic toxicity
- irreversible grade 3 thrombocytopenia at least possibly due to flavopiridol.
- And is a drug related event with an attribution of possible, probable or definite.

Patients with compromised bone marrow function from lymphoma will not be evaluable for hematologic related DLT. Irreversible is defined as lasting > 3 weeks. All toxicity will be evaluated and scored using NCI Common Terminology Criteria for Adverse Events (CTCAE) version 3.0 until December 31, 2010. CTCAE version 4.0 will be utilized beginning January 1, 2011.

3.3 TREATMENT MODIFICATIONS:

Patients should have recovered toxicities that are clinically significant and attributable to flavopiridol to grade 1 or baseline before beginning another cycle. If toxicity has not resolved to this level within 3 weeks from the end of the previous cycle, flavopiridol will be discontinued.

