3.4 STUDY CALENDAR

Studies	Pre-therapy^A	Day -1 or day 1 of each cycle	Weekly during therapy	Every second cycle	Follow-up^B
Hx; PE; VS; PS	x	x			x
Tumor Measurement	x			x	x
CBC/diff	x ^F	x	x		x
Electrolytes, Creatinine/BUN ALT, AST, Bilirubin, LDH, Ca ⁺⁺ , Phos, Mg	x ^F	x	x		x
10 mL red top for serum storage	x	x			x
Clinical PET scan ^D	x				
CT chest/abdomen/pelvis ^C	x			x	x
Bone marrow biopsy & aspirate and peripheral blood for flow cytometry where indicated ^E	x			x ^E	
Tumor biopsy, timed blood collections and/or apheresis ^G	x				
Tumor Lysis Syndrome monitoring		x ^H			

- A- Initial assessment may be performed within 4 weeks prior to starting treatment.
- B- Follow-up to occur every 3-4 months until disease progression requiring initiation of non-protocol therapy.
- C- Extent of CT scans may be limited to assess sites of prior disease.
- D- PET scans will be performed pre-therapy if clinically indicated. PET may be obtained at the first post-treatment restaging in patients in CR.
- E- Obtain pre-treatment and after patients achieve CR by other staging.

F- These laboratory tests must be obtained within one week of initial treatment.

G- Where possible, tumor biopsies will be obtained by core needle biopsy or surgery pre-treatment. In select patients a repeat core biopsy of superficial nodes may be carried out within 24 hours from the end of the first flavopiridol infusion. Snap freeze and store tissue biopsies for translational studies at -80°C. Lymphapheresis may be performed pre-treatment in patients with leukemic MCL and may be repeated after the completion of the flavopiridol infusion. Timed blood samples of 20-40 mL each, typically pre-treatment, at 1 hour, 3hours, 6hours and 24hours may be obtained in selected patients during the first flavopiridol infusion. In patients with leukemic disease this may be repeated during the second flavopiridol infusion. Research blood collections will be limited to less than 450 mL in any 6 week period.

H- Please refer to section 4.3.6 on TLS monitoring for details of what is required.

- **Pharmacokinetics:** Collect one 6 mL sodium heparin tube at the following time points on dose 1 and 2 of cycle 1 only: 30 minutes after the start of the bolus infusion, 4.5 hours and 6 hours after the start of the bolus infusion. All PKs should be placed directly on ice and then refrigerated until specimen is picked up.

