6 STATISTICAL CONSIDERATIONS

This will be a Phase I/II study.

- The Phase I portion of the study will have three to four treatment dose levels. Three to six patients will be accrued on each of the dose levels. Enrollment will proceed on the next dose level if 0 of 3 or 1 of 6 patients experience DLT. MTD will be defined as the highest dose level in which 0-1/6 patients experience DLT.
- The Phase II portion of the study will use a Simon optimal two-stage design in each of the two histology cohorts, MCL and DLBCL. For each of these two, the trial will be designed to rule out a 20% response rate ($p_0=0.20$) in favor of a 45% response rate ($p_1=0.45$). The justification for this is that other regimens could be associated with a 20% response rate and the objective is to demonstrate if this agent is superior to that level. With $\alpha=\beta=0.10$, the first stage for each histology would accrue 14 patients (28 total for the first stage, but by performing response evaluation on the 6 patients treated at the MTD in the phase I portion of the study and by counting them in each phase II arm according to their histology, this would only require 22 newly enrolled patients in the first stage). If 0-

3 of the 14 in a given arm have a PR or CR, then no further patients would be accrued. If 4 or more of the 14 patients in an arm have a CR or PR, then accrual would proceed to a total of 25 patients in that arm (11 more patients beyond the 14 in the first stage). If 4 to 7 have a PR or CR, then this is insufficient activity to warrant further investigation while 8 or more responses in 25 would be adequate to justify further development. Under the null hypothesis, 20%, the probability of early termination would be 70%.

- With up to 24 patients enrolled in the phase I portion, and 50 - 6 (6 are used for response evaluation from the phase I portion)=44 new patients potentially required for the phase II portion, a total of 24+44=68 total evaluable patients may be required if both arms need to go to the second stage. To allow for a small number of non evaluable patients, the accrual ceiling will be set at 71.
- To determine if patients have responded, they will be assessed every 8 weeks. The latest time for determining a response will be after 16 weeks or 4 cycles of therapy.
- It is expected that up to 3 years may be required to accrue up to 71 total patients permitted to enroll onto this trial.

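### For a responder treated on schedule, the 4-week off-drug condition in section 5.3 cannot be established by the response deadline in section 6

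*Combined protocol and SAP*

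**What the plan says.** Section 5.3 adopts published lymphoma response criteria with modifications, and the first modification is a condition on duration: "Responses must last for at least 4 weeks off treatment". It precedes the definitions of CR and PR, which are the events counted in section 6.

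Treatment does not stop on response. The Précis says "Continue if CR, PR or SD for up to 6 cycles", and sections 3.2.1 and 3.2.2 say "Administer up to 6 cycles if no disease progression". Each cycle is four weekly doses followed by two weeks without drug, six weeks in all. On imaging, section 3.2.2 says "Restage all positive sites of disease after every 2 cycles". After treatment, footnote B of the study calendar (section 3.4) applies: "Follow-up to occur every 3-4 months until disease progression requiring initiation of non-protocol therapy". The calendar includes tumor measurement and CT at those visits.

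Section 6 sets a different clock: "To determine if patients have responded, they will be assessed every 8 weeks", and "The latest time for determining a response will be after 16 weeks or 4 cycles of therapy". In each histology, 4 or more CR/PR in 14 opens the second stage, and 8 or more in 25 justifies further development.

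No section says what off treatment means for a patient who is still being dosed, or that the follow-up scans serve to confirm response.

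**The concern.** Response rate is a primary objective (section 1.1.1), and both decisions in each arm depend on a count of responders. Section 5.3 makes a response countable only after a drug-free period. Section 6 closes the count while a responder is still scheduled for treatment. If both are applied as written, an on-schedule responder cannot be confirmed by the closing date.

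Two careful analysts could then report different counts from the same data. Consider a patient in PR at the week-12 and week-24 restagings who progresses in cycle 5. Under section 5.3 read literally, this patient never had four weeks of response off drug and is a non-responder. Under the section 6 window, the same patient is a responder. At stage 1, one such patient can decide whether an arm closes.

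**Working it through.** **Timeline.** Inputs: doses on days 1, 8, 15 and 22 of a 42-day cycle and up to 6 cycles (sections 3.2.1 and 3.2.2); 28 days off treatment (5.3); limit of 16 weeks or 4 cycles (6).

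- Longest planned dose gap: day 22 to day 43 = 21 days, less than 28. Within a cycle the gap is 7 days.
- Cycle 4: last dose 3 × 42 + 22 = day 148; cycle ends 4 × 42 = day 168. At that point the patient is 168 − 148 = 20 days off drug, with the next dose due on day 169.
- Cycle 6: last dose 5 × 42 + 22 = day 232. Four weeks off drug: 232 + 28 = day 260, which is (260 − 1)/7 = 37 weeks after the first dose.
- Against the 4-cycle limit: 260 − 168 = 92 days late, about 13 weeks. Against the 16-week limit: 37 − 16 = 21 weeks late.

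The section 6 limit is also inconsistent within itself: 4 cycles × 6 weeks = 24 weeks, not 16, and restaging every 2 cycles is every 12 weeks, not 8. Correcting that alone would not remove the conflict, because at the end of cycle 4 the patient is still only 20 days off drug.

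**The plan's design, reproduced.** With X ~ Bin(14, p) in stage 1 and Y ~ Bin(11, p) in stage 2:

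- P(stop early) = P(X ≤ 3)
- P(declare active) = Σ over x = 4 to 14 of P(X = x) · P(Y ≥ max(0, 8 − x))

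At p = 0.20, early stopping is 0.698 (the plan says 70%) and P(declare active) is 0.093. At p = 0.45, early stopping is 0.063 and P(declare active) is 0.903. A search for the optimal design at α = β = 0.10 returns the same rules (3/14, 7/25). The sample-size calculation is sound.

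**Illustration of what the definition could do.** Let f be the share of CR/PR patients who would not meet the literal 4-week off-drug rule. The documents give no value, so a range is shown. Two further assumptions are made: 20% and 45% are rates before the rule is applied, and f is the same at both.

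| f | 0.45(1 − f) | Early stop | Declare active | 0.20(1 − f) | Early stop | Declare active |
|---|---|---|---|---|---|---|
| 0 | 0.450 | 0.063 | 0.903 | 0.20 | 0.698 | 0.093 |
| 10% | 0.405 | 0.117 | 0.811 | 0.18 | 0.765 | 0.056 |
| 20% | 0.360 | 0.198 | 0.674 | 0.16 | 0.826 | 0.030 |
| 30% | 0.315 | 0.311 | 0.500 | 0.14 | 0.879 | 0.014 |

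Power and type I error fall together.

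**The case against.** The strongest defence is that the condition is deliberate. It stands among declared modifications, and requiring persistence off drug is strict but coherent. Section 6 could then be read as limiting when a response may first appear, with duration settled later. That reading would reconcile the two sections, but neither states it, and section 6 speaks of determining response, not of its onset. The defence shows that a consistent reading exists; it does not show that the plan has adopted it.

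A reader might infer that the endpoint cannot be met at all. The documents do not support that:

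- A patient who completes 6 cycles and is still in response at a follow-up scan meets the definition, as can one who stops early in response.
- Section 3.3 allows up to 3 weeks of recovery after a cycle ends, so a dose gap can reach 21 + 21 = 42 days, although no scan is scheduled to use it.
- The restaging after cycle 6 has no fixed day. If done at the end of that cycle (day 252) it falls 20 days after the last dose; done 8 days later, it would reach day 260.

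A reader might also take the table as the plan's actual loss of power. That does not follow either. If 45% already means response as section 5.3 defines it, power remains 0.90. If it does not, the loss in power comes with a lower false-positive rate.

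**Conclusion.** The contradiction stands. For a responder treated on schedule through six cycles, four weeks off treatment is first reached at about week 37, some 13 weeks after the 4-cycle limit. The response counted in the 4/14 and 8/25 rules cannot be established for that patient when section 6 says it is. The sections also disagree on outcome for anyone whose response is lost on treatment after the 4-cycle assessment.

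The timing result rests on the stated schedule without delays. The size of any effect on the operating characteristics is unknown. Under the assumptions above, f of 10%, 20% or 30% would take power from 0.90 to 0.81, 0.67 or 0.50, and type I error from 0.093 to 0.056, 0.030 or 0.014. The defect lies in what is counted and when, not in the sample size. Because it concerns a primary endpoint and both decision rules, it should be reconciled before any responder count is made.

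**What to change.** Three changes, best made in one revision:

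1. **Section 5.3.** Replace the off-treatment sentence with a rule that a countable CR or PR is one lasting at least 4 weeks from first documentation, whether or not treatment is continuing.
2. **Section 6.** State that this is the response counted in the 4/14 and 8/25 rules, that the 4-cycle limit applies to first documentation, and that confirmation may come after it. The last clause is needed: a response first seen at the week-24 restaging is confirmed at week 28 at the earliest, or at week 36 if the next scheduled restaging is used. Bring the 8-week and 16-week figures into line with the 6-week cycle at the same time.
3. **Reporting.** Present persistence off drug separately, as response duration.

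The cost is a few sentences and possibly some imaging. Scheduled restagings are 12 weeks apart, so relying on the next one would in effect demand about 12 weeks of persistence. Confirming at 4 weeks may need a repeat scan in some responders, and the stage 1 count must wait for late confirmations. Persistence off drug would no longer be part of the primary endpoint. If the sponsor does want it there, the alternative is to keep the condition, name the assessment that establishes it, move the section 6 limit accordingly, and state that 20% and 45% refer to that endpoint.

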2 ELIGIBILITY ASSESSMENT AND ENROLLMENT

2.1 ELIGIBILITY CRITERIA

- 2.1.1 Previously treated mantle cell lymphoma or diffuse large B-cell lymphoma (to include mediastinal (thymic) large B-cell lymphoma; transformed large B-cell lymphoma; follicular grade IIIB large B-cell lymphoma; intravascular large B-cell lymphoma)
- 2.1.2 Confirmed pathological diagnosis at the National Cancer Institute, NIH.
- 2.1.3 Recurrent measurable disease (measurable disease in 2 dimensions or leukemic disease which can be quantified and followed)
- 2.1.4 Prior anthracycline-based treatment for patients with DLBCL
- 2.1.5 Age > 18years
- 2.1.6 ECOG performance 2 or better
- 2.1.7 Major organ function: ANC > 1000/mcL, Platelet > 50,000/mcL, Creatinine < 1.5 mg/dL or creatinine clearance > 60 mL/min; SGPT < 5 x upper limit of normal; bilirubin < 2 mg/dL (total) except < 5 mg/dL in patients with Gilbert's syndrome as defined by > 80% unconjugated. ANC and platelet requirements must be met independent of transfusion.
- 2.1.8 Informed consent and willingness to use contraception by both men and women.
- 2.1.9 Both male and female patients must be willing to use adequate contraception (to include effective barrier methods of contraception) or to completely abstain from heterosexual intercourse while on protocol treatment.
- 2.1.10 Not pregnant or nursing because of an unknown potential for teratogenic or abortifacient effects
- 2.1.11 HIV serology negative. HIV positive patients receiving combination anti-retroviral therapy are excluded from the study because of possible pharmacokinetic interactions with flavopiridol. Additionally, the biology of HIV associated DLBCL's is often quite different from HIV negative disease due to involvement of EBV.
- 2.1.12 Hepatitis B surface antigen negative.
- 2.1.13 No active CNS lymphoma. These patients have a poor prognosis and because they frequently develop progressive neurological dysfunction that would confound the evaluation of neurological and other adverse events.
- 2.1.14 No history of inflammatory bowel disease unless this has been inactive for a period of 2 or more years.
- 2.1.15 Recovery from toxicity of prior therapy to a grade 1 or less.
- 2.1.16 No systemic cytotoxic or experimental treatments within 4 weeks of treatment.
- 2.1.17 No WBC > 100,000 cells/mcL

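### Read literally, Section 5.3 has no progression item for a growing sole mass, a growing extranodal lesion or a new extranodal lesion, so these count as stable disease

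*Combined protocol and SAP*

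**What the plan says.** Section 5.3 takes published lymphoma response criteria (reference 18), says they are modified, and prints its own definitions. Progressive disease is "Defined by at least one of the following":

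- items 1 and 2, with a threshold of 25% or more on the first: "increase in the sum of the products of at least two lymph nodes, appearance of new lymph nodes"
- item 3, at 50% or more: "increase in the size of the liver and/or spleen as determined by measurement below the respective costal margin"
- item 4: "appearance of new palpable hepatomegaly or splenomegaly that was not previously present"
- item 5, at 50% or more: "increase in the absolute number of circulating lymphocytes"

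Stable disease "will be characterized by not meeting any of the criteria outlined above". A partial response needs a fall of at least 50% in the sum of products over the six largest nodes or masses, regression of liver and spleen nodules by at least 50%, no growth of nodes, liver or spleen, and no new disease site. A response has to hold for at least four weeks off treatment.

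Section 2.1.3 asks for disease measurable in two dimensions, or quantifiable leukemic disease, and sets no minimum number of nodes. Section 2.1.1 widens the DLBCL group "to include mediastinal (thymic) large B-cell lymphoma; transformed large B-cell lymphoma; follicular grade IIIB large B-cell lymphoma; intravascular large B-cell lymphoma". On treatment, the précis says "Continue if CR, PR or SD for up to 6 cycles", and Sections 3.2.1 and 3.2.2 allow up to six cycles in the absence of progression.

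**The concern.** The progression list is narrower than the disease the trial admits and narrower than its own partial-response text. A new extranodal lesion blocks a partial response but does not make progression, because the progression list counts only new lymph nodes. A patient with one measurable mass has no second node to enter the sum in item 1. Since stable disease takes everything left over, clear growth of these kinds is recorded as stability.

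At stake are the split between stable and progressive disease, time on treatment, the progression-based end of follow-up (Section 3.4 note B and Section 3.6), and the marker analysis in Section 12.5 that uses stable disease as an outcome. Whether the primary response count is exposed needs a separate check.

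**Working it through.** **1. The plan's own design figures.** Inputs from Section 6: p0 = 0.20, p1 = 0.45, 14 then 25 patients per histology, stop at 3 or fewer of 14, fail at 7 or fewer of 25.

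- Early termination at p0: P(X ≤ 3 | 14, 0.20) = 0.698, against 70% stated.
- Probability of passing: sum over x = 4 to 14 of P(X = x | 14, p) × P(Y ≥ 8 − x | 11, p). This is 0.0933 at p0 and 0.9026 at p1, which meets α = β = 0.10.

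X and Y count complete and partial responses only. Stable and progressive disease are both non-response, so moving a patient between them changes neither count nor boundary.

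**2. Cases against the printed definitions**, assuming no new nodes, no liver or spleen enlargement and no lymphocyte rise:

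| Finding | Progression item met | Partial response | Literal class |
|---|---|---|---|
| Sole measurable mass grows | None; no second node | Excluded, no 50% fall | Stable |
| Known extranodal lesion grows, nodes stable | None | Excluded, no 50% fall | Stable |
| New extranodal lesion | None | Excluded, new site | Stable |
| Known extranodal lesion outside liver and spleen grows, nodes fall by at least 50% | None | Not excluded | Partial response |
| One mass grows, second measured node stable | Item 1 once the sum is up 25% | Excluded | Progressive or stable, by the sum |

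**3. How far item 1 reaches.** It applies to a sum, so both nodes need not grow. If the growing mass is a share s of the starting sum and the rest is stable, the mass must grow by 0.25/s:

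- s = 0.90: 27.8%
- s = 0.75: 33.3%
- s = 0.50: 50%
- s = 0.25: 100%

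With one mass and no second node, the item cannot be met at any growth.

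**4. Primary count.** The fourth row of the table is the only literal route by which the gap adds a response. One such patient could turn 3 of 14 into 4, or 7 of 25 into 8. The documents give no frequency for it.

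**5. Time on treatment.** Restaging after every two cycles (Sections 3.2.1 and 3.2.2) means 2 × 6 = 12 weeks and 2 × 4 = 8 infusions to the next assessment. If the gap applied at every restaging from the end of cycle 2, cycles 3 to 6 would allow 4 × 4 = 16 infusions. Section 6 instead gives assessments every 8 weeks. On four weeks of dosing and two off, an eight-week span holds at most 6 infusions (for example weeks 1 to 4, 7 and 8).

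**6. Patients exposed.** The documents give no share with a sole mass or extranodal-only disease. Assuming 10% to 30% for illustration, 0.10 × 25 = 2.5 and 0.30 × 25 = 7.5 patients per histology. This counts exposure, not error: each must also progress without meeting any other item. Patients with nodal disease who first progress by a new extranodal lesion come on top and cannot be counted.

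**The case against.** Five arguments can be made for the text as it stands.

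- **Three of the five items are not nodal, and item 1 is a sum.** This stands. It confines the gap to patients with no second measured node and to progression that is only extranodal, but none of the three other items covers those cases in general.
- **The published criteria may fill the gap.** Section 5.3 says they apply as modified, then prints a complete progression list and a residual stable class. Whether unprinted elements survive cannot be settled from the documents. That is a reason to state it, since a reader following the printed text arrives at stable disease.
- **Little depends on the stable/progressive split.** This largely stands. Section 1.1 has no objective for progression-free survival, time to progression, response duration or disease control. Section 1.2.5.3 calls the marker work exploratory, and Section 6 plans no defined analysis for it.
- **Treatment need not continue.** Section 3.5 lets the physician withdraw a patient, so continuation is permitted and not certain. Progression itself is not among the off-study criteria there.
- **The limited imaging would miss new lesions anyway.** Note C to the calendar lets CT be restricted to sites of earlier disease, and Section 2.2 has brain imaging only when clinically indicated. This stands as a limit on any correction.

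A reader might infer more: that lost responses would stand and so favor the drug. The text does not support this in general. The four-week requirement does not refer to the progression list. A responder with a new site no longer meets the partial-response text, and reappearance of detectable disease ends a complete response. Only the growing known extranodal lesion outside the liver and spleen escapes. A reader might also infer that Section 12.5 pools responders with stable patients as a favorable group; it names both outcomes but does not say they are pooled.

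**Conclusion.** The gap is real on the printed text: three kinds of progression meet no item and fall into stable disease, in conflict with the partial-response wording and with eligibility that does not require two nodes. It is a classification defect and does not threaten the primary design. The boundaries 3/14 and 7/25 and the error rates stand, and the effect on the response count is small, through one literal route. The main effects are on the stable/progressive split, time on treatment (up to 8 infusions per two-cycle restaging interval), the end of follow-up, and the exploratory stable-disease correlation.

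This rests on reading Section 5.3 literally, with the cited criteria not filling what the printed list omits. The number of patients affected is unknown; the 2.5 to 7.5 per histology is an assumed range of exposure. The documents do not support saying that every growing single mass is scored stable, or that such patients will certainly stay on treatment.

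**What to change.** Reconcile the progression, partial-response and stable-disease definitions in Section 5.3 with one another and with Sections 2.1.1 and 2.1.3, so that growth of a sole mass, growth of an extranodal lesion and a new extranodal site can each be classified as something other than stable disease. Include the case of a known extranodal lesion growing while nodes shrink, which neither the partial-response nor the progression text now excludes. State whether elements of the cited criteria that are not printed still apply. Then reconcile the result with the continuation wording in the précis and Sections 3.2.1 and 3.2.2, and with note C to the study calendar. The choice of clinical rule is for the sponsor and the investigators.

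The cost is mainly protocol wording; sample size and decision boundaries do not change. Some patients now classed as stable would become progressive. Wording alone will not secure detection, because CT limited to earlier sites may not show every new one.
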